#### Duke Raleigh/Macon Pond (Duke Women's Cancer Care Raleigh)

Patients will also be enrolled and will receive treatment at the Duke Raleigh Macon Pond location (Duke Women's Cancer Care Raleigh). The study's research coordinators will perform all study-related duties and do not anticipate needing the assistance of the Duke Raleigh clinical research team.

#### Adverse Events/Safety Reporting

The study team will maintain an adverse event log to track any adverse incidents and will also report these to the IRB for record-keeping purposes. Specifically, the study team will look for cases of post-procedural syncope, heavy bleeding, or reaction to TENS unit for a week following the biopsy; any subject will be offered study withdrawal. Any need for hospitalization or death that is probably study related will be immediately reported to the IRB as a UPIRTSO; we expect none of these cases to be study-related. The PI will review and assess frequency, severity and relevancy to the study of all AEs on an ongoing basis throughout the duration of the trial. Tri-monthly reviews by the PI will be completed as a more comprehensive review to look for AE trends.

#### Study Duration

We estimate we will stop enrolling new participants in October 2023 or if we reach 160 consents, whichever comes first.

IRB Number: Pro00111100

NCT05472740

Study Title: Transcutaneous electric nerve stimulation for analgesia during outpatient endometrial biopsy: a randomized controlled trial (TENS RCT)

PI: [name]

Study Location: Duke University

V1.9 Approval Date: 08/23/2023

We plan to conduct a superiority trial. Prior research has established that a 25-30% reduction in overall pain or a 13-15 mm decrease in VAS represent clinically significant differences in pain scores. We determined a standard deviation of 30 mm as based on a prior similar study by Yilmazer et al. We will conservatively plan for a sample size sufficient to detect a 15 mm reduction in pain scores in the intervention group as compared to the control group. We would need 64 subjects in each group for a total of 128 subjects to attain 80% power at alpha = 0.05 level of significance, which corresponds to a Cohen's d around 0.50 (moderate reduction). We hope to recruit 160 participants for this trial to account for an assumed attrition rate of 20%.

Data will be recorded using Research Electronic Data Capture (REDCap). Pain will be measured along discrete intervals including: speculum placement, tenaculum placement, immediately after biopsy, removal of speculum, 5 minutes after biopsy and 15 minutes after biopsy. The primary outcome will be pain score immediately after biopsy. The primary outcome will be compared between treatment arms using linear regression adjusting for baseline pain. Secondary outcomes include pain score at other intervals, patient tolerability and acceptability, and provider's satisfaction with the procedure. All testing will be performed at a two-tailed significance level of 0.05.

As there is no standard analgesia option, patients may be offered pain medication prior to the procedure such as ibuprofen. While this would not be a contraindication to enrollment, we anticipate adequate block randomization for this to normalize in both groups, and we will note what form of analgesia was used during our statistical analysis. We believe there is an important value to allow providers to continue their normal standard of care options.

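### Does calling the 15 mm target conservative mean that the trial is underpowered for its own range of clinically significant differences?

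*SAP*

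**What the plan says.** The sample-size paragraph of the SAP sets out two alternative criteria: "a 25-30% reduction in overall pain or a 13-15 mm decrease in VAS represent clinically significant differences in pain scores". It takes an SD of 30 mm from an earlier similar study and then says: "We will conservatively plan for a sample size sufficient to detect a 15 mm reduction in pain scores in the intervention group". The result is: "We would need 64 subjects in each group for a total of 128 subjects to attain 80% power at alpha = 0.05". This is raised to 160 recruited for 20% attrition. The SAP makes tests two-sided: "All testing will be performed at a two-tailed significance level of 0.05".

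The analysis is specified as follows: "The primary outcome will be compared between treatment arms using linear regression adjusting for baseline pain". No correlation between baseline and outcome enters the sample size. The control-group mean is not stated. The Protocol, under Study Duration, limits recruitment: "We estimate we will stop enrolling new participants in October 2023 or if we reach 160 consents, whichever comes first".

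**The concern.** Within a range of differences that all count as clinically significant, the cautious choice for sample size is the smallest, because it needs the most patients. The SAP picks the largest value in its millimetre range and calls the choice conservative. Read that way, the label is backwards.

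What would be at stake is the reading of a non-significant result. Someone who relied on the adverb might think the trial had power to spare across 13 to 15 mm. On the SAP's inputs and an unadjusted test, a true 13 mm benefit would be missed about 32% of the time with 128 evaluable patients, against 20% for a true 15 mm benefit. Even with all 160 evaluable, power at 13 mm falls just short of 80%. Because enrolment may stop by date, 160 is a ceiling.

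**Working it through.** **Inputs (SAP, sample-size paragraph).** Target difference 15 mm; SD 30 mm; two-sided alpha 0.05; power 80%; equal arms; attrition 20%. Millimetre range 13 to 15 mm; alternative criterion 25-30%.

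**1. Reproduce the plan's figure.** The normal approximation per arm is n = 2(z₀.₉₇₅ + z₀.₈₀)² × SD² / δ².

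- At 15 mm: 2 × (1.960 + 0.842)² × 900 / 225 = 62.8, rounded up to 63.
- The two-sample t-test (noncentral t) gives 63.8, rounded up to 64. Power at 64 per arm is 80.1%.
- Total 2 × 64 = 128. With attrition, 128 / 0.8 = 160.
- Effect size 15 / 30 = 0.50.

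Every stated figure reproduces.

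**2. Same calculation across the millimetre range (t-test, SD 30 mm, unadjusted).**

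| True difference | n per arm for 80% | Power, 64 per arm | Power, 72 per arm | Power, 80 per arm |
|---|---|---|---|---|
| 13 mm | 84.6 → 85 | 68.2% | 73.3% | 77.8% |
| 14 mm | 73.1 → 74 | 74.5% | 79.4% | 83.5% |
| 15 mm | 63.8 → 64 | 80.1% | 84.6% | 88.2% |

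A check at 13 mm by the normal approximation: the standard error is 30 × √(2/64) = 5.30 mm; 13 / 5.30 − 1.96 = 0.49; power is 68.8%, close to the t-test value. The smallest difference with 80% power is 15.0 mm at 64 per arm and 13.4 mm at 80 per arm. So within 13 to 15 mm, 15 mm is the least demanding choice.

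**3. The other criterion.** A percentage reduction becomes millimetres only through the control mean M, which the documents do not give. Taking M as an assumption:

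- 30% of M equals 15 mm at M = 15 / 0.30 = 50 mm.
- 25% of M equals 15 mm at M = 15 / 0.25 = 60 mm.
- Below 50 mm, 15 mm exceeds the whole 25-30% range. Between 50 and 60 mm it lies inside it. Above 60 mm it is smaller than the whole range.
- At an assumed M of 70 mm, the range is 0.25 × 70 = 17.5 mm to 0.30 × 70 = 21 mm.

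Against this criterion, 15 mm may or may not be cautious. The documents do not settle it.

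**4. Effect of the planned adjustment.** If baseline pain has correlation r with the outcome, the residual SD is 30 × √(1 − r²). The values of r are assumptions.

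- r = 0.3: SD 28.6 mm; power at 13 mm is 72.2% (64 per arm) or 81.5% (80 per arm).
- r = 0.5: SD 26.0 mm; power at 13 mm is 80.2% or 88.2%.
- Power of 80% at 13 mm needs r of about 0.50 with 128 evaluable, or about 0.23 with 160.

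**5. What the analysis will show in any case.** The unadjusted 95% confidence interval has half-width 10.5 mm with 128 evaluable and 9.4 mm with 160. With 128, a non-significant observed reduction above 13 − 10.5 = 2.5 mm leaves 13 mm inside the interval, and one above 15 − 10.5 = 4.5 mm leaves 15 mm inside. The interval from the planned regression therefore shows directly whether a relevant effect has been excluded.

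**The case for a change.** The strongest case for a change is that the adverb qualifies the planning of the sample size, where its meaning is settled, and that it sits next to a range that contradicts it. The 20% inflation is not spare power, since it only restores 128 evaluable patients. Baseline adjustment cannot be relied on either: no correlation is assumed, and the listed pain assessments are "speculum placement, tenaculum placement, immediately after biopsy, removal of speculum, 5 minutes after biopsy and 15 minutes after biopsy", none of which is labelled as a baseline. The remedy would cost only a sentence.

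Part of this stands. Against the millimetre range the adverb is unsupported, and the power figures at 13 and 14 mm are right. The gain from adjustment is only a possibility, and the conclusion does not depend on it.

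The rest does not carry a change. The feared misreading is hard to sustain, because the sentence with the adverb itself names 15 mm and the next ties 80% power to an effect size of about 0.50. Nothing in the SAP promises power at smaller differences. The 25-30% criterion leaves open a reading in which 15 mm is the cautious target. The 68% figure assumes the full 20% loss, whereas the primary outcome is recorded immediately after the biopsy, in the same visit; losses could be smaller, though the documents do not establish this.

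**Conclusion.** No change to the plan is needed. The choice of 15 mm is a legitimate target within the SAP's own range, and the sample size delivers the 80% power claimed for it. What remains is a loosely used adverb: against 13 to 15 mm it points the wrong way, while against 25-30% it could be justified if the control mean were above 60 mm.

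The size of the matter is a power of about 68% at 13 mm with 128 evaluable patients, rising to 78% with 160. This assumes an SD of 30 mm and an unadjusted two-sided test at 0.05; any correlation of baseline pain with the outcome would raise it. Since the SAP makes no claim at 13 mm, these figures refute nothing it says. Rewording would correct no number, move no patient and change no result, and the planned regression already supplies the interval a reader needs to judge a non-significant finding.

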## **Design and Procedures**

### Patient selection

We will conduct a double-blind, placebo-controlled randomized controlled trial. We will recruit patients over 18 years of age who are undergoing an outpatient endometrial biopsy at Duke gynecologic oncology and general gynecology clinics. Our exclusion criteria include age younger than 18 years, unable to follow study instructions and/or independently adjust TENS settings, cutaneous damage at the TENS application site, any electronic implanted device, inability to understand or declines to sign the informed consent form, and previous personal experience using a TENS unit. We also will not enroll patients who are undergoing a concurrent procedure at the time of biopsy (ie. they're having a biopsy and an IUD placed). Pregnant women will be excluded from the study as a part of the standard of care before having an endometrial biopsy, therefore a pregnancy test may be done for reproductive-aged women. Endometrial biopsy is used to detect endometrial hyperplasia and cancer, however we expect fewer than 15% of patients to be diagnosed with endometrial cancer.

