#### Short form translation

Spanish-speaking patients may also be included using a certified medical Spanish interpreter and a bilingual adult witness using a short-form Spanish consent. Spanish-speaking patients will have survey questions interpreted by the medical Spanish interpreter; our surveys will not be interpreted into Spanish prior. The interpreter will interpret and accompany Spanish-speaking patients throughout the entire procedure. The bilingual adult witness may be a clinician, if needed. The clinician will not be affiliated with this study and will not be on KP.

Given that many endometrial biopsies will be determined as part of the workup during a visit for abnormal uterine bleeding, eligible patients will be introduced the study at the time of determination for an endometrial biopsy. Participants will have the entirety of time from introduction of study to starting the procedure to decide whether to enroll, and can withdraw from the study at any time.

After informed consent, participants will be randomized to either the active TENS arm or the placebo TENS arm. Randomization will occur in Redcap using a schema provided by the statistician. Participant demographics and clinical information will be collected on a standardized survey in RedCap including self-reported age, race, ethnicity, level of education, history of previous endometrial biopsy, medical history, daily narcotic, or anxiolytic use. Pre-procedural anxiety will be assessed via a 100 mm visual analogue scale with 0 mm being “no anxiety at all” and 100 being “the most anxious I have ever been”.

As there is no standard analgesia option, patients may be offered pain medication prior to the procedure such as ibuprofen. While this would not be a contraindication to enrollment, we anticipate adequate block randomization for this to normalize in both groups, and we will note what form of analgesia was used during our statistical analysis. We believe there is an important value to allow providers to continue their normal standard of care options.

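### A prespecified enrolling-clinic term in the primary model would be a nearly free gain in precision; the planned analysis is valid without it

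*SAP*

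**What the plan says.** The Protocol (Patient selection) recruits patients "undergoing an outpatient endometrial biopsy at Duke gynecologic oncology and general gynecology clinics". A later section (Duke Raleigh/Macon Pond) adds a further place of enrolment: "Patients will also be enrolled and will receive treatment at the Duke Raleigh Macon Pond location".

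Both documents state that there is no standard analgesia and that patients may be offered medication such as ibuprofen. The choice rests with providers: "We believe there is an important value to allow providers to continue their normal standard of care options". The plan expects block randomisation to even out analgesia between arms and will note which form was used. It does not say that analgesia enters the primary model.

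The Protocol says that allocation is made in REDCap from a schema supplied by the statistician. Neither document names a stratification factor.

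The SAP's analysis paragraph gives one primary model: "The primary outcome will be compared between treatment arms using linear regression adjusting for baseline pain". No clinic, location or provider term appears. The primary outcome is the VAS pain score immediately after biopsy, and "All testing will be performed at a two-tailed significance level of 0.05".

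**The concern.** Patients from several clinic settings are pooled, and something that affects pain is left to local practice. Mean biopsy pain could therefore differ by clinic for reasons unrelated to TENS. If it does, leaving clinic out has two effects:

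- The between-clinic variation stays in the residual, so the standard error is larger than it need be.
- If by chance one arm holds more patients from a higher-pain clinic, the estimate carries that difference unadjusted.

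The plan's reliance on blocking does not deal with this. Blocks without clinic strata balance the arm totals, not the clinic mix or analgesia use within arms. Clinic is fixed before randomisation and should be known for every patient, so it is a natural covariate that the model does not use.

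**Working it through.** **Inputs from the SAP.** Difference: "sample size sufficient to detect a 15 mm reduction in pain scores in the intervention group". SD: "We determined a standard deviation of 30 mm". Size: "We would need 64 subjects in each group for a total of 128 subjects to attain 80% power at alpha = 0.05". Testing is two-sided.

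**Inputs assumed.** The documents give no clinic sizes, number of clinics or between-clinic pain differences. Everything below that needs them is illustrative.

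**1. The plan's own figures.** The standardised difference is 15/30 = 0.50. The two-sample t-test needs 63.77 per arm, so 64 per arm and 128 in total. Power at 64 per arm is 80.1%. With 20% attrition, 128/0.80 = 160. All of these reproduce.

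**2. Precision, with 30 mm read as the total SD.** If a fraction f of the variance lies between clinics, a clinic term leaves a residual SD of 30 × √(1 − f). The standard error is approximately that SD × √(2/64).

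| f | Residual SD (mm) | SE (mm) | Power for 15 mm, 64 per arm |
|---|---|---|---|
| 0 | 30.0 | 5.30 | 80.1% |
| 0.05 | 29.24 | 5.17 | 82.1% |
| 0.10 | 28.46 | 5.03 | 84.1% |

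In terms of clinic means, take three clinics with shares of 40/40/20%:

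- Offsets of 0/5/10 mm give a between-clinic variance of 14 mm², residual SD 29.8 mm and power 80.8%.
- Offsets of 0/10/20 mm give 56 mm², 29.1 mm and 82.6%.
- Offsets of 0/15/30 mm give 126 mm², 27.8 mm and 85.7%.

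The gain therefore runs from under 1 to nearly 6 percentage points.

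**3. Validity without a clinic term.** Least-squares analyses of 10,000 simulated trials per scenario (shares 40/40/20%, 64 per arm, unstratified allocation, total SD 30 mm) gave:

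- Offsets 0/10/20 mm: type I error 4.8% without clinic and 4.9% with it; mean estimate −15.0 mm in both models; empirical SE 5.35 and 5.20 mm; power 79.5% and 81.4%.
- Offsets 0/5/10 mm: power 79.5% in both models.

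**4. How often clinics are unbalanced, and what it does in mm.** Take 160 patients in clinics of 60/60/40, allocated in unstratified blocks of 4, so 80 per arm. A 10-point difference in a clinic's share is 8 patients (8/80), and a 15-point difference is 12 patients (12/80). Counting whole patients over 40,000 simulated allocations, some clinic differs by 10 points or more in about 46% of trials, and by 15 points or more in about 15%.

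Converted to the pain scale with offsets 0/10/20 mm:

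- Mean offset = 0.375 × 0 + 0.375 × 10 + 0.25 × 20 = 8.75 mm.
- Between-clinic variance = 0.375 × 100 + 0.25 × 400 − 8.75² = 60.9 mm².
- SD of the shift in the estimate = √(60.9 × 2/80) = 1.23 mm, which the simulation confirms (1.24 mm).

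So imbalance in shares is common, but its usual effect is about 1.2 mm against a 15 mm target.

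**The case against.** The strongest reply is that this is a preference about covariates, not a defect. Much of that stands.

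- **Validity.** A reader might infer that the TENS estimate is biased or the test invalid. It is neither: randomisation makes the estimate unbiased on average, type I error is nominal, and the unadjusted standard error already allows for chance imbalance.
- **Power.** A reader might infer that the trial is underpowered. That needs 30 mm to be a within-clinic SD. Adding clinic variance would then lower power to 79.5%, 77.7% or 74.8% for the three sets of offsets in step 2. The SAP does not describe its SD that way. If 30 mm is a total SD, the planned 80% already carries the clinic variance.
- **Size.** No between-clinic difference is documented. With 60/60/40 clinics equally spaced in pain, a 10% share needs about 24 mm between the extremes, more than the treatment effect sought. The upper end of the range is generous.
- **Premises.** It is tempting to say that the clinics differ in case mix and operators, or that there are exactly three of them. The documents say neither. They refer to clinics in the plural, and the Raleigh location is itself a women's cancer care site.
- **Analgesia.** It is left to providers, so clinic is only a proxy for it. The plan will note analgesia, and the Protocol (Outcome Measures) lists medication use, anxiety and sociodemographic factors as possible correlates of pain. That handling is more direct for analgesia, but it is a secondary question and defines no term in the primary model.
- **Baseline pain.** It might absorb part of a clinic difference. However, the listed VAS time points include no pre-procedure pain score, so this cannot be counted on.

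What survives is narrow: a pre-randomisation variable that may explain some variance is left out, at almost no saving.

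**Conclusion.** This is a free improvement in precision. It is not an error in the plan's validity or in its stated power. The supported facts are that several clinic settings are pooled, analgesia is at provider discretion, no strata are named, and the primary model has no clinic term.

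The benefit depends on an unknown clinic variance. It is close to nothing if clinics differ little, about 2 to 4 power points if 5% to 10% of the variance lies between clinics, and nearly 6 points at the widest offsets tried. Protection against realised imbalance is worth about 1.2 mm (SD) at offsets of 0/10/20 mm, under the illustrative clinic sizes.

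A reader might also infer that the planned confidence interval is too wide because a stratification factor is omitted. That follows only if allocation was stratified by clinic, which the documents neither state nor exclude.

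**What to change.** Before unblinded analysis, amend the SAP's primary model sentence so that the linear regression has fixed effects for arm and enrolling clinic, alongside the baseline covariate already planned. Define the clinic levels as those actually used for enrolment, and state in advance how a clinic with very few patients would be merged.

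State whether the REDCap schema was stratified by clinic. If it was, the stratum must be in the model, because leaving it out would make the interval too wide. If it was not, the term is optional but still worth having.

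The cost is one SAP sentence and one degree of freedom per additional clinic: two if there are three levels, which is negligible with 128 patients. Randomisation does not change. If unblinded results have already been seen, report the clinic-adjusted model as a sensitivity analysis and keep the planned model as primary, since a later change could look data-driven.

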#### Intervention

Participants will be randomly assigned either to the active TENS group or the placebo TENS group via the Redcap randomization tool. We will attempt to blind both the patient and the provider to the intervention. The clinical research coordinator helping with placement, teaching, and operation of the TENS unit will not be blinded. Clinical coordinators will read from a prepared script that will be the same for the placebo and intervention arms. A Spanish-speaking patient will have the script interpreted to them by a certified medical Spanish interpreter. A TENS 7000 that is FDA-approved will be used for this project. TENS units will be placed parallel to the vertebral column at the T-10-L1 and S2-S4 levels as done in previous studies.

Prior to applying the TENS pads to the patient, the study coordinators will ensure the TENS unit has been set to the determined, standardized frequency. The patient will be able to adjust the intensity.

All subjects will have four TENS pads placed on their backs. Those in the active TENS group will have all four electrodes connected to all four pads by the study coordinator. Those in placebo TENS group will have

only two electrodes (one electrode from each wire) connected to two pads. The remaining two electrodes (one from each wire) will be covered with a tight-fitting cap. The subjects can still turn on and adjust the device, just as they would if they were in the active TENS group.

The TENS will be initially turned onto a low frequency by the clinical coordinator. This will be standardized for all patients. The patient will then be told to individually adjust the intensity to each patient's maximum sensory level, or when they feel a strong tingling sensation that is not painful. Patients will be told to maintain the stimulation at the maximum non-painful level and to increase the intensity if they are experiencing pain during the procedure. The TENS will start 5 minutes prior to the procedure and continue until 5 minutes after the completion of the procedure. The provider will be blinded to the patients' group allocations as they will enter the room after initiation of TENS.

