#### Outcome Measures

The primary outcome will be pain at the time of endometrial biopsy; we hypothesize that participants in the active TENS group will have reduced pain scores compared to placebo group. Pain scores will be collected using a 0-100 mm visual analogue scale (VAS) with 0 mm being "no pain" and 100 mm being "worst pain imaginable" during the procedure to be collected by the clinical coordinator. VAS scores will also be collected at the following discrete times: speculum placement, tenaculum placement, immediately after biopsy, removal of speculum, 5 minutes after biopsy and 15 minutes after biopsy.

Patients and providers will fill out a post-evaluation survey including post-procedural symptoms and questions to assess tolerability and acceptability of the biopsy procedure. Secondary outcomes include pain scores at other intervals throughout the procedure, satisfaction with the biopsy, and whether certain factors (anxiety level at the time of biopsy, medication use, sociodemographic factors) are correlated with higher pain scores. Patients will also be asked if they thought they were in the placebo group or the treatment group, and whether they would choose the same pain control if they had to have another EMB. Providers will be asked to evaluate ease of procedure on a 100 mm scale and to estimate perceived pain during the procedure on a 100 mm VAS scale. All information will be collected in RedCap.

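### The primary model leaves out the anxiety score the trial already collects: a minor missed gain in precision, alongside analgesia wording that needs clarifying

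*SAP*

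**What the plan says.** **Primary model.** The SAP, in the paragraph on outcomes and testing, states: "The primary outcome will be compared between treatment arms using linear regression adjusting for baseline pain". It names no other covariate. The sample-size paragraph assumes an SD of 30 mm and mentions no adjustment.

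**Anxiety.** In the Protocol, under Short form translation: "Pre-procedural anxiety will be assessed via a 100 mm visual analogue scale". Under Outcome Measures, the secondary outcomes include "whether certain factors (anxiety level at the time of biopsy, medication use, sociodemographic factors) are correlated with higher pain scores".

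**Timing.** The Protocol text puts allocation ahead of the survey: "After informed consent, participants will be randomized to either the active TENS arm or the placebo TENS arm". Under Intervention: "The TENS will start 5 minutes prior to the procedure and continue until 5 minutes after the completion of the procedure".

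**Analgesia.** The last paragraph of the SAP anticipates "adequate block randomization for this to normalize in both groups, and we will note what form of analgesia was used during our statistical analysis". The Protocol section Short form translation carries the same sentence: "we anticipate adequate block randomization for this to normalize in both groups". On the method of allocation, the Protocol says only: "Randomization will occur in Redcap using a schema provided by the statistician". No stratification factor is described in either document.

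**The concern.** A baseline variable related to pain takes variance out of the error term when it enters the regression, and it corrects for chance imbalance between arms. The trial already collects such a candidate and asks, as a secondary question, whether it tracks pain. Leaving it out of the primary model may give up precision that needs no new data.

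The analgesia sentence invites a second look because blocking without stratification only keeps the arm sizes close and does nothing specific for analgesic use. To say that the form will be noted also leaves open whether it will be tabulated, adjusted for or tested.

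What is at stake is the width of the confidence interval for the primary comparison and the clarity of the plan. Bias is not at stake.

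**Working it through.** **Inputs from the SAP.** Difference 15 mm, SD 30 mm, 64 per arm, two-sided alpha 0.05, 20% attrition.

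**Reproducing the plan's figure.** The unadjusted SE is 30 × √(2/64) = 5.30 mm. By the noncentral t, power is 79.5% at 63 per arm and 80.1% at 64 per arm, so 64 is right. Recruitment is 128 / (1 − 0.20) = 160, also right.

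**Adding anxiety.** Let R² be the share of within-arm variance in pain that anxiety explains. The documents give no value, so a range is assumed. The SE is 30 × √(1 − R²) × √(2/64) / √(1 − q) on 125 degrees of freedom. Here q is the chance R² of arm on anxiety, averaged over a Beta(0.5, 63) distribution. This charges the model for the lost degree of freedom and for chance correlation between anxiety and arm.

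| R² (correlation r) | Mean SE, mm | Power | Unadjusted n per arm with the same power |
|---|---|---|---|
| no covariate | 5.30 | 80.1% | 64 |
| 0% (0) | 5.32 | 79.8% | 63.5 |
| 1% (0.10) | 5.30 | 80.2% | 64.1 |
| 5% (0.22) | 5.19 | 81.8% | 66.8 |
| 10% (0.32) | 5.05 | 83.8% | 70.4 |
| 20% (0.45) | 4.76 | 87.8% | 79.1 |

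Break-even is at R² of about 0.8% (r about 0.09).

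**With a valid baseline pain score also in the model.** Suppose baseline pain explains 10% (an assumption), which alone gives 83.8%. Only what anxiety explains beyond baseline pain then counts, and that is usually less than it explains alone. If it adds 0%, 1%, 2.5%, 5% or 10%, power is 83.5%, 83.9%, 84.5%, 85.5% or 87.5% (124 degrees of freedom, q from Beta(1, 62.5)).

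**Blocking and analgesia.** In a simulation with 128 patients and 50% analgesic use (assumed), the SD of the between-arm difference in use is 0.088 with blocks of four and 0.089 with simple randomisation. Blocking therefore adds essentially no balance. By formula, the SD is √(2 × 0.25/64) = 8.8 percentage points. With an assumed analgesic effect of 5, 10 or 15 mm, an imbalance of one SD shifts the estimate by 0.44, 0.88 or 1.33 mm. Divided by 5.30 mm, that is 0.08, 0.17 or 0.25 SE, and the SE already allows for it.

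**Analgesia as the only covariate.** Its R² is p(1 − p) × effect² / 900, where p is the proportion using it. For effects of 5, 10 and 15 mm, power is 80.0%, 80.5% and 81.4% at 20% use, and 80.1%, 80.9% and 82.3% at 50% use.

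**The case against.** The strongest reply is that nothing here is wrong. The test is valid, 64 per arm delivers the stated power with no covariate at all, and adding one more covariate is a matter of preference. The Protocol poses the anxiety–pain relation as an open question and does not assert it. The net effect in the table runs from a loss of 0.3 point to a gain of 7.7 points (87.8 − 80.1). All of this stands, and it is why the point is minor.

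The timing objection also stands in part. The survey is described after allocation, Outcome Measures speaks of anxiety at the time of biopsy, and the coordinator who places and teaches the device is not blinded. A rating taken late could reflect the intervention or the coordinator's manner, so anxiety belongs in the primary model only on the condition given in the fix.

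A late change to a primary model has a cost in credibility. The SAP is V1.9, dated 08/23/2023, and the Protocol expects enrolment to stop in October 2023 or at 160 consents.

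A reader might infer from the analgesia sentence that the comparison is exposed to bias from unequal analgesic use. The documents do not support that: randomisation balances use on average whether or not it is blocked, and chance imbalance is covered by the SE. A reader might also infer that allocation is unstratified. The schema is not in the documents, so one can say only that no stratification is described.

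**Conclusion.** Minor, and worth doing because it is cheap. The primary model omits a collected variable that the Protocol itself names as a possible correlate of pain. The gain is conditional: nothing useful if anxiety explains about 1% of the variance or less, 1.7 points of power at 5% (81.8 − 80.1), and 3.7 points at 10% (83.8 − 80.1). These figures rest on the SAP's own 15 mm, 30 mm and 64 per arm, and on an assumed range for R². Where a valid baseline pain score is in the model, the gain depends on what anxiety adds to it.

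It would go too far to conclude that the trial is underpowered or its primary test biased; neither follows from the documents. The analgesia sentence credits the wrong mechanism and leaves the reporting undefined, but its numerical consequence is at most about a quarter of an SE for a one-SD imbalance under the assumptions above.

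The documents give no collection time for baseline pain. That is a separate issue and lends no weight to this one.

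**What to change.** Before outcomes are compared by arm:

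1. Check when the anxiety VAS was recorded for enrolled patients. If it was before TENS was started, and preferably before the patient or the unblinded coordinator could act on the allocation, add it to the primary linear regression. If this cannot be confirmed, use it only in a sensitivity analysis.
2. Fill a missing anxiety value with the overall mean, ignoring arm, so that no patient is dropped.
3. Where anxiety enters the primary model, report the model without it as a sensitivity analysis.
4. In both the SAP and the Protocol, keep the statement that randomisation is blocked, since this sentence is its only mention. Add that randomisation, not blocking, balances analgesic use on average, and that the form of analgesia will be tabulated by arm. Keep analgesia out of the primary model: it offers little, and its timing relative to allocation is not stated.

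**Cost.** One model sentence in the SAP, one clarified sentence in each document, and a check of recording times. If anxiety is unrelated to pain, power falls by about 0.3 point (80.1% to 79.8%). The change to the primary model is late and must be dated and documented. Sample size and patient care do not change, and the anxiety score is already collected.
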